4.3.4 Continued Access to AT-527

Currently, the Sponsor does not have any plans to provide IMP (RO7496998 [AT-527]) or any other study treatments to patients who have completed the study. The Sponsor may evaluate whether to continue providing AT-527 in accordance with the Roche Global Policy on Continued Access to Investigational Medicinal Product, available at the following website:

http://www.roche.com/policy_continued_access_to_investigational_medicines.pdf

4.4 CONCOMITANT THERAPY

Concomitant therapy consists of any medication (e.g., prescription drugs, over-the-counter drugs, vaccines, herbal or homeopathic remedies, nutritional supplements) used by a patient in addition to protocol-mandated treatment from 7 days prior to initiation of study drug (12 months for COVID-19 vaccines) to the end of study telephone call (Day 33). All such medications should be reported to the investigator and recorded on the Concomitant Medications eCRF.

4.4.1 Permitted Therapy

Patients are permitted to use the following therapies during the study:

- Hormonal contraceptives (see Section 4.1.1)
- Hormone-replacement therapy
- Paracetamol (acetaminophen)
- Non-steroidal anti-inflammatory drugs
- COVID-19 vaccines are permitted from Day 15 onwards (see Section 4.5.2 for documentation requirements pertaining to vaccine type and date of dosing).
 - Patients must have a 40-day window since their last dose of vaccination (second dose if applicable) prior to enrollment.

4.4.2 Cautionary Therapy

4.4.2.1 Herbal Therapies

Concomitant use of herbal therapies is not recommended because their pharmacokinetics, safety profiles, and potential drug–drug interactions are generally unknown.

4.4.2.2 Effects of Co-administered Therapies on AT-511 and Metabolites

P-glycoprotein (P-gp) inhibitors

- *Concomitant use of P-gp inhibitors is permitted but dosing of study drug and the P-gp inhibitor must be staggered by 2 hours (with study drug dosed first).*

Common examples of P-gp inhibitors include carvedilol, imidazoles, macrolides, ritonavir and verapamil.

*For a list of P-gp inhibitors, refer to
<https://go.drugbank.com/categories/DBCAT002667>*

Breast Cancer Resistance Protein (BCRP) inducers

- BCRP inducers may affect plasma levels of AT-229. However, AT-229 is considered an inactive metabolite, and changes in AT-229 PK are not expected to affect the antiviral activity of AT-527. Consider substituting or stopping drugs that are major BCRP inducers during study treatment and resume 12 hours after the final dose of study drug. In the event that the BCRP inducers cannot be safely discontinued or substituted, they should be used with caution. Common examples of BCRP inducers include venlafaxine.*

*For a list of BCRP inducers, refer to
<https://go.drugbank.com/categories/DBCAT003986>.*

Organic Anion Transporter 1 and 3 (OAT1 and OAT3) inhibitors

- OAT1 and OAT3 inhibitors may affect plasma levels of AT-273. However, AT-273 is considered an inactive metabolite, and changes in AT-273 PK are not expected to affect the antiviral activity of AT-527. Consider stopping drugs that are major OAT1/3 inhibitors during study treatment and resume 12 hours after the final dose of study drug. In the event that the OAT1/3 inhibitors cannot be safely discontinued or substituted, they should be used with caution. Common examples of OAT1/3 inhibitors include furosemide, losartan and cimetidine.*

*For a list of OAT1 and OAT3 inhibitors, refer to
<https://go.drugbank.com/categories/DBCAT004041> and
<https://go.drugbank.com/categories/DBCAT003946>, respectively.*

4.4.2.3 Effects of AT-511 on Co-administered Therapies

P-glycoprotein (P-gp) sensitive substrates

- P-gp inhibition: In the event that sensitive substrates of P-gp with a NTI cannot be safely discontinued or substituted, they should be dosed 2 hours after study drug administration, by which time absorption of AT-511 is considered essentially complete. Common examples of P-gp sensitive substrates with NTI include digoxin and tamoxifen.*

*For a list of sensitive P-gp substrates with NTI refer to
<https://go.drugbank.com/categories/DBCAT004027>.*

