Appendix 5: COVID-19 Symptom Diary and Patient Global Impression of Severity

	Same as usual / no change	Not as good as usual / no sense
13. Rate your sense of smell since you got up this morning.		
14. Rate your sense of taste since you got up this morning.		

Patient Global Impression of Severity

Please rate your overall COVID-19 symptoms at their worst since you got up this morning.

None

Mild

Moderate

Severe

Appendix 6

Update on AT-527 Reproductive Toxicity, In Vitro, and Clinical Drug–Drug Interaction Data

New data from reproductive toxicity studies have become available since the release of the AT-527 Investigator's Brochure Version 7. The new data are summarized below. Overall, these new data did not provide new safety concerns and support further development including the planned Phase 3 clinical trial.

In vitro drug–drug interaction (DDI) flags for AT-527 with potential clinical relevance as well as preliminary data from clinical DDI studies were taken into account in the concomitant therapy section.

REPRODUCTIVE TOXICITY

The potential for reproductive toxicity was assessed in dose range-finding and pivotal Good Laboratory Practice (GLP)-compliant embryofetal development studies in rats and rabbits and in a GLP-compliant fertility study in the rat.

EMBRYOFETAL DEVELOPMENT

Definitive GLP-compliant embryofetal development (EFD) studies did not reveal evidence of teratogenicity or embryofetal toxicity up to the highest maternal dose level tested of 1000 mg/kg/day in rats and 100 mg/kg/day in rabbits.

Administration of AT-527 by oral gavage to female rats at dose levels of 250, 500, and 1000 mg/kg/day once daily from gestation day (GD) 7 to GD17 in an initial dose range-finding study and in a subsequent definitive study induced no maternal or developmental toxicity at any dose level.

In a dose range finding EFD study in pregnant rabbits, the two highest dose groups of 500 and 250 mg/kg/day were terminated prematurely due to severe maternal toxicity. The low dose level of 125 mg/kg/day was tolerated, but induced maternal toxicity characterized by apparent reductions of food consumption, minimal body weight loss and slightly reduced gravid uterine weight. There were no external fetal abnormalities at 125 mg/kg/day and resorption incidence was not noticeably increased, but fetal weight was reduced by 10%, which was secondary to maternal toxicity.

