then a 2 mg midazolam dose (1 mL) is administered 2 hours (± 5 minutes) later (at approximately the same time when midazolam was administered in Day 1). A second 550 mg AT-527 dose is administered in the evening, approximately 12 hours after the AT-527 morning dose.

Preliminary results

- Assessment 1 (Day 3 is compared to Day 1). The below figure presents the changes in pharmacokinetic parameters (C_{max} , AUC, and half-life) for midazolam (left) and 1-hydroxy-midazolam (right) in the presence of AT-527 (single dose of 550 mg). In each forest plot, the changes in pharmacokinetic parameters are presented after the simultaneous (Arm-1; top) and staggered (Arm-2; bottom) administration of midazolam.

[figure not shown]
Legend to the figure. AUC: area under the plasma concentration-time curve, CI: confidence interval, Cmax: maximum plasma concentration, HL: half-life, SD: single dose, 1-OH midazolam: 1-hydroxy midazolam, GMR: geometric mean ratio.

A single dose of AT-527 increased the exposure of midazolam by 20–25% after simultaneous or staggered dosing. The exposure of 1-hydroxy midazolam was slightly increased by 25–30% after simultaneous dosing, and minimally increased by 5–15% after staggered dosing.

- Assessment 2 (Day 7 is compared to Day 1). The below figure presents the changes in pharmacokinetic parameters (C_{max} , AUC, and half-life) for midazolam (left) and 1-hydroxy-midazolam (right) in the presence of AT-527 (multiple doses of 550 mg). In each forest plot, the changes in pharmacokinetic parameters are presented after

Appendix 6: Update on AT-527 Reproductive Toxicity, In Vitro, and Clinical Drug–Drug interaction Data

the simultaneous (Arm-1; top) and staggered (Arm-2; bottom) administration of midazolam.

[figure not shown]
Legend to the figure. AUC: area under the plasma concentration-time curve, CI: confidence interval, Cmax: maximum plasma concentration, HL: half-life, SD: single dose, 1-OH midazolam: 1-hydroxy midazolam, GMR: geometric mean ratio.

Multiple doses of AT-527 increased the plasma exposure of midazolam by 90% (simultaneous dosing) and by 60% (staggered dosing), and had a slight to minimal effect on 1-hydroxy midazolam (an increase of 20–25% after simultaneous dosing, and an increase of 0–10% after staggered dosing).

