A single dose (simultaneous or staggered) of AT-527 increased the exposure of midazolam by 20–25%. AT-527 (AT-511) is a weak competitive inhibitor of CYP3A4.

Appendix 6: Update on AT-527 Reproductive Toxicity, In Vitro, and Clinical Drug–Drug interaction Data

Multiple doses of AT-527 increased the exposure of midazolam by 90 and 60% after simultaneous and staggered (30% less) dosing, respectively. This is consistent with time-dependent inhibition of CYP3A4.

Staggered dosing after single or multiple doses of AT-527 had limited effect on the PK parameters of midazolam.

The induction potential of AT-511, while confronted by a more pronounced time-dependent inhibition effect, is weak and unlikely to affect (reduce) the efficacy of hormonal contraceptives that are substrates of CYP3A4.

CYP3A4 substrates can be co-administered with AT-527 without dose adjustment. Staggered dosing of AT-527 is not warranted.

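### Appendix 6 clears all CYP3A4 substrates after a 60–90% rise in midazolam exposure: a caution for narrow therapeutic index drugs and a 550 mg BID limit are worth adding

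*Protocol*

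**What the plan says.** The interaction data are in Protocol Appendix 6, Study AT-03A-009. After one dose: "A single dose of AT-527 increased the exposure of midazolam by 20–25% after simultaneous or staggered dosing". After repeated dosing: "Multiple doses of AT-527 increased the plasma exposure of midazolam by 90% (simultaneous dosing) and by 60% (staggered dosing". The data interpretation attributes the repeated-dose result to time-dependent inhibition of CYP3A4. It remarks that "Staggered dosing after single or multiple doses of AT-527 had limited effect on the PK parameters of midazolam" and concludes that "CYP3A4 substrates can be co-administered with AT-527 without dose adjustment", adding that staggering is not warranted. The one clinical consequence it discusses is induction, judged "unlikely to affect (reduce) the efficacy of hormonal contraceptives that are substrates of CYP3A4".

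The introduction to Appendix 6 says that "preliminary data from clinical DDI studies were taken into account in the concomitant therapy section". Section 4.4 has no entry for CYP3A4 substrates. Section 4.4.2.3, on the effects of AT-511 on other drugs, has a single entry, which opens "P-gp inhibition: In the event that sensitive substrates of P-gp with a NTI cannot be safely discontinued or substituted" and then asks for the substrate to be taken 2 hours after study drug. Section 3.1 caps the AT-527 dose at 1100 mg BID for 5 days. The SAP does not bear on this point.

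**The concern.** The protocol accepts that NTI drugs need separate handling when AT-511 inhibits P-gp. For CYP3A4 it has a measured rise in the exposure of a co-administered drug, at a dose and duration close to the trial's own course, and makes no such distinction. Induction, the consequence it discusses, would lower exposure. Overexposure, which is what was observed, is not discussed for drugs with a small safety margin.

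The clearance also carries no AT-527 dose limit, although all the midazolam data come from 550 mg. At stake is the safety of any patient taking a sensitive CYP3A4 substrate with a NTI late in the 5-day course. A site reading Appendix 6 would find nothing that separates that patient from others.

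**Working it through.** **Inputs** (Protocol Appendix 6, Study AT-03A-009, unless stated)
- AT-527 550 mg: two doses on study Day 3, BID on Days 4–6, morning dose on Day 7. Midazolam is given with the Day 7 morning dose (Arm 1) or 2 hours after it (Arm 2), 12 subjects per arm.
- Midazolam, Day 3 vs Day 1: +20–25%.
- Midazolam, Day 7 vs Day 3: +45–60% simultaneous, +15–35% staggered.
- Midazolam, Day 7 vs Day 1: +90% simultaneous, +60% staggered.
- Trial course: 10 doses over about 5 days (Section 4.3.2); maximum 1100 mg BID (Section 3.1).

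**Step 1: place in the course.** Doses before the Day 7 morning = 2 + 3 × 2 = 8. The Day 7 morning dose is the ninth, on the fifth dosing day (Days 3, 4, 5, 6, 7). The comparison therefore represents the end of the trial's 10-dose course.

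**Step 2: reproduce the reported rise.** The chained ratio (Day 3/Day 1) × (Day 7/Day 3) should bracket Day 7/Day 1.
- Simultaneous: 1.20 × 1.45 = 1.74 to 1.25 × 1.60 = 2.00. The reported 1.90 lies inside.
- Staggered: 1.20 × 1.15 = 1.38 to 1.25 × 1.35 = 1.69. The reported 1.60 lies inside.

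The appendix's figures agree with one another.

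**Step 3: what the stagger achieves.** Share of the rise that remains = 60/90 = 0.67. This compares two separate arms of 12, whose Day 1 midazolam exposure already differed by 10–20%. Each percentage is a change from the same arm's Day 1, which removes much of that difference, but 0.67 is still a rough figure. Appendix 6 itself draws the same qualitative conclusion about staggering.

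**Step 4: dose coverage.** Maximum permitted over tested dose = 1100/550 = 2.0. Appendix 6 shows no midazolam data above 550 mg.

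**Step 5: the two inhibition routes side by side.**

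| | P-gp | CYP3A4 |
|---|---|---|
| Entry in Section 4.4.2.3 | Yes, for sensitive NTI substrates | None |
| First option | Stop or substitute | None |
| Fallback | 2-hour stagger | None |
| Rationale for the stagger | AT-511 absorption essentially complete by then | Not applicable: 60% rise remained |

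A drug that is both a P-gp and a CYP3A4 substrate could come under the first column. The external P-gp list is not part of the documents, so the overlap cannot be checked. Even then, the stagger is weak mitigation for the CYP3A4 component.

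**The case against.** The strongest reply is that this is a stated decision. Appendix 6 records that the net CYP3A4 effect was uncertain from in vitro work, reports a dedicated study with its results in full, names the mechanism and draws a conclusion. A reader might infer that the missing CYP3A4 entry contradicts the claim that the data were taken into account in Section 4.4. It does not: a decision that no entry was needed is consistent with that claim.

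A reader might also infer that affected patients go unwatched. The documents do not support that.
- Medication changes are recorded at each visit (Section 4.5.2), and adverse events are sought at each contact (Section 5.3.1).
- Investigators can exclude patients who could not safely take part (Section 4.1.2) and must stop study treatment when safety is at risk (Section 4.6.1).
- Cohorts B–E have coagulation tests on Days 1, 3 and 7 (Appendices 2 and 3).
- Sites are also referred to the Investigator's Brochure, which was not available for this check.

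None of these is specific to the interaction, but together they limit its consequences.

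Section 4.4.2.2 offers caution wording even though "AT-229 is considered an inactive metabolite, and changes in AT-229 PK are not expected to affect the antiviral activity of AT-527". That contrast is suggestive, but it concerns effects on AT-527's metabolites and does not show that Section 4.4.2.3 is wrong.

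Finally, stopping a NTI drug for a short course has its own risks, so a call to withhold such drugs would go further than the evidence. What survives is narrow: no passage justifies extending the clearance to NTI drugs, or to AT-527 doses that were not tested with midazolam.

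**Conclusion.** The point holds as a low-cost improvement to consider. The measured size is a midazolam exposure ratio of 1.9 (simultaneous) or 1.6 (staggered) on the fifth dosing day of 550 mg BID. These results are preliminary, with 12 subjects per arm, and the forest plots with their confidence intervals were not available for this check. A rise below 2-fold may be acceptable for most CYP3A4 substrates; the point concerns only those with a NTI.

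Two stronger readings are tempting and not supported. One is to project a rise for other drugs: this needs each drug's dependence on CYP3A4, which the documents do not give. The other is to assume a larger effect at 1100 mg BID: the documents do not show that such a dose was selected, and they have no midazolam data there, so the effect is unknown.

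The documents name no NTI CYP3A4 substrate and do not say how many patients take one. The virology endpoint is not affected.

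**What to change.** 1. Add an entry to Section 4.4.2.3:

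> Sensitive CYP3A4 substrates with a NTI: use with caution. The investigator should review such drugs at screening and monitor clinically at the Day 3, 5 and 7 visits and at the Day 14 contact, with any dose change left to the treating physician. A 2-hour stagger is not sufficient mitigation.

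2. In Appendix 6, limit the statement that no dose adjustment is needed to substrates without a NTI and to AT-527 550 mg BID.

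The entry does not ask for the NTI drug to be withheld. The Day 14 contact is included because the documents do not show how soon the inhibition wears off after the last dose.

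The cost is a few lines of text, with no new visit, sample or laboratory test: Day 14 is already a telephone call in Cohorts A–D and a visit in Cohort E. The downside is some extra investigator attention for patients on such drugs. Where visits are made by mobile nurses, findings would have to be passed to the investigator.

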4.4.3 Prohibited Therapy

Use of the following concomitant therapies is prohibited from Day 1 until study completion or early termination, except as otherwise indicated, as described below:

- Investigational therapy (other than protocol-mandated study treatment) is prohibited within 90 days prior to initiation of study treatment and during study treatment*
- Sofosbuvir, for patients with active HCV*

- Abacavir, for patients with HIV
- Hydroxychloroquine or amiodarone within 3 months prior to screening and during the study

4.5 STUDY ASSESSMENTS

The schedules of activities to be performed during the study are provided in [Appendix 1–Appendix 3](#). All activities should be performed and documented for each patient.

Patients will be monitored for safety and tolerability throughout the study.

At applicable sites, informed consent may be obtained and certain study assessments may be performed by a mobile nursing (MN) professional at the patient's home to improve access and convenience for patients participating in the study. If participating sites cannot provide MN services, the Sponsor will select a healthcare organization that will be responsible for providing MN services (the MN vendor). The site or MN vendor is responsible for ensuring that all MN professionals are licensed, qualified, and in good standing, as per applicable regulations, and that appropriate background checks have been performed. If the investigator at a participating site determines that MN services are appropriate for a patient and the patient gives written or electronic informed consent to participate in MN visits, the MN network will communicate with the patient and the patient's site. MN visits will be scheduled on specified visit days, to allow for the relevant assessments to be performed by the MN professional. The schedule of activities will specify the assessments that can be performed by an MN professional.

4.5.1 Informed Consent Forms and Screening Log

Written or electronic informed consent for participation in the study must be obtained before performing any study-related procedures (including screening evaluations). Informed Consent Forms for enrolled patients and for patients who are not subsequently enrolled will be maintained at the study site.

All screening evaluations must be completed and reviewed to confirm that patients meet all eligibility criteria before enrollment. The investigator will maintain a screening log to record details of all patients screened and to confirm eligibility or record reasons for screening failure, as applicable.

4.5.2 Medical History, Baseline Conditions, Concomitant Medication, and Demographic Data

Medical history, including clinically significant diseases, surgeries, cancer history (including prior cancer therapies and procedures), reproductive status, smoking history, and use of alcohol and drugs of abuse, will be recorded at baseline. In addition, all medications (e.g., prescription drugs, over-the-counter drugs, vaccines, herbal or

homeopathic remedies, nutritional supplements) used by the patient within 7 days prior to initiation of study treatment (12 months for COVID-19 vaccines) will be recorded. At the time of each study visit and at the follow-up telephone call (Day 33), an interval medical history should be obtained and any changes in medications and allergies should be recorded.

Demographic data will include age, sex, and self-reported race/ethnicity.

COVID-19 vaccines should be reported by the brand name or company manufacturer, if available (examples: Pfizer COVID-19 vaccine, Moderna COVID-19 vaccine) and date administered if known. If not available, report as COVID-19 vaccine.

4.5.3 Physical Examinations

A complete physical examination, performed at screening and other specified visits, should include an evaluation of the head, eyes, ears, nose, and throat, and the cardiovascular, dermatologic, musculoskeletal, respiratory, gastrointestinal, genitourinary, and neurologic systems. Any abnormality identified at baseline should be recorded on the General Medical History and Baseline Conditions eCRF.

Limited, symptom-directed physical examinations should be performed as clinically indicated. Changes from baseline abnormalities should be recorded in patient notes. New or worsened clinically significant abnormalities should be recorded as adverse events on the Adverse Event eCRF.

4.5.4 Vital Signs

Vital signs will include measurements of respiratory rate, pulse rate, and systolic and diastolic blood pressure and SpO₂ while the patient is in a supine or seated position, and temperature. Record abnormalities observed at baseline on the General Medical History and Baseline Conditions eCRF. At subsequent visits, record new or worsened clinically significant abnormalities on the Adverse Event eCRF.

4.5.5 Laboratory, Biomarker, and Other Biological Samples

At screening only, samples for the following laboratory tests will be sent to the study site's local laboratory for analysis:

- Pregnancy test (*urine or serum*)
All women of childbearing potential will have a pregnancy test at screening
- SARS-CoV-2 diagnostic test (RT-PCR or rapid antigen test) at screening: nasopharyngeal swab
- Hematology: WBC count, RBC count, hemoglobin, hematocrit, platelet count, and differential count (neutrophils, eosinophils, basophils, monocytes, lymphocytes, other cells)
- Chemistry panel (*serum or plasma*): bicarbonate or total carbon dioxide (if considered standard of care for the region), sodium, potassium, chloride, glucose,

BUN or urea, creatinine, *creatinine clearance (Cockcroft-Gault formula)*, total protein, albumin, phosphate, calcium, magnesium, total and direct bilirubin, ALP, ALT, AST, triglycerides, cholesterol, amylase and lipase

On all other study days, samples for the following laboratory tests will be sent to designated central laboratories for analysis, unless otherwise noted:

- Hematology: WBC count, RBC count, hemoglobin, hematocrit, platelet count, and differential count (neutrophils, eosinophils, basophils, monocytes, lymphocytes, other cells)
- Chemistry panel (serum or plasma): bicarbonate or total carbon dioxide (if considered standard of care for the region), sodium, potassium, chloride, glucose, BUN or urea, creatinine, *creatinine clearance (Cockcroft-Gault formula)*, total protein, albumin, phosphate, calcium, magnesium, total and direct bilirubin, ALP, ALT, AST, urate, CK (isoenzyme analysis if CK is elevated), cardiac troponins, BNP, triglycerides, cholesterol, amylase, LDH, PCT, and lipase
- Coagulation: INR, aPTT, PT, D-dimer, and fibrinogen
- Plasma samples for PK analysis and exploratory PK research
- Serum samples for PD analysis and exploratory biomarker research
- Serum samples for SARS-COV-2 antibody titer and serum viral load
- Nasopharyngeal swab, saliva, and blood samples for SARS-COV-2 virology tests (viral load and exploratory analysis, including sequencing)
- Nasopharyngeal swab sample for respiratory pathogen co-infections panel (multiplex assay)
- Nasosorption™ samples for exploratory research on biomarkers
- Saliva samples for exploratory research on biomarker (viral) assay development
- Blood PAXgene RNA for RNA sequencing or quantitative polymerase chain reaction
- Cryopreserved peripheral blood mononuclear cells (PBMCs) for high dimensional cytometry analysis
- Plasma obtained during PBMC processing will be retained for further exploratory research

Exploratory biomarker research and virologic testing may include, but will not be limited to, analysis of inflammatory mediators and/or cytokines, immune cells, serum viral load, SARS-COV-2 antibody titer, and virus genotypic analysis. Research may also involve extraction of DNA, cell-free DNA, or RNA; analysis of mutations, single nucleotide polymorphisms, and other genomic variants; and genomic profiling through use of next-generation sequencing of a comprehensive panel of genes. Genomic research will be aimed at exploring inherited characteristics.

For sampling procedures, storage conditions, and shipment instructions, see the laboratory manual.

Biological samples will be destroyed no later than the time of completion of the final Clinical Study Report, with the following exceptions:

- Plasma samples collected for PK analysis may be needed for additional PK assay development and validation; therefore, these samples will be destroyed no later than 5 years after the final Clinical Study Report has been completed.
- Blood (serum, PMBCs, plasma [from PBMC processing]), blood PAXgene RNA, nasopharyngeal swabs, nasosorption and saliva samples collected for biomarker research and biomarker (viral) assay development will be destroyed no later than 15 years after the final Clinical Study Report has been completed.

When a patient withdraws from the study, samples collected prior to the date of withdrawal may still be analyzed, unless the patient specifically requests that the samples be destroyed or local laws require destruction of the samples. However, if samples have been tested prior to withdrawal, results from those tests will remain as part of the overall research data.

Data arising from sample analysis, including data on genomic variants, will be subject to the confidentiality standards described in Section [8.4](#).

Given the complexity and exploratory nature of exploratory biomarker analyses, data derived from these analyses will generally not be provided to study investigators or patients unless required by law. The aggregate results of any conducted research will be available in accordance with the effective Sponsor policy on study data publication.

